COMIRB Protocol

COLORADO MULTIPLE INSTITUTIONAL REVIEW BOARD
[name] [contact] [contact]

Protocol #: 13-2819

Project Title: Treatment of tracheostomy granulomas

Principal Investigator: [name]

Version Date: 12/07/2016

I. Hypotheses and Specific Aims:

Specific Aims:

Examine standard of care by comparing the effectiveness of different treatments of tracheostomy granulomas: steroid application, silver nitrate, betadine.

Hypotheses:

We surveyed the thirteen attending doctors at Children's Hospital Colorado and the satellite clinic in Colorado Springs, CO regarding which method of treatment they deem as most successful. The most commonly reported preferred method of treatment was silver nitrate (75%). We hypothesize that treatment with steroid application or betadine may result in less frequent recurrence of tracheostomy granulomas compared to silver nitrate use.

II. Background and Significance:

The incidence of tracheostomy granulation tissue is between 10-80% of all tracheostomy tubes^{1,2,3}. Granulation tissue can cause bleeding, difficulty with tracheostomy tube changes, and respiratory distress if it occludes the end of the tracheostomy tube. Reports of death due to obstruction from granulation tissue exist¹. There is no significant data on the best course of treatment to prevent granulation tissue and to remove granulation tissue once it develops^{1,2}. The purpose of this study is to evaluate treatment of tracheostomy granulation tissue and determine if any significant difference in the frequency and extent of granulation tissue formation with different topical treatments. Each treatment has minimal morbidity and side effects. Granulation tissue is caused by fibroblasts, collagen and blood vessels formed in the proliferative phase of healing. Suggested causes of hypergranulation include prolonged inflammation from infection, foreign body irritation, external friction, and allergens. Studies have shown that steroid treatment is effective in treating granulation tissue. Silver nitrate works as chemical cautery by reacting with water in the blood and forming nitric acid⁴. Anti-septic solutions, such as betadine, are known to be toxic for fibroblasts and also help with chronic low-grade infections, and therefore, are helpful in treatment of granulation tissue⁵.

III. Preliminary Studies/Progress Report:

To our knowledge, none of the faculty in the pediatric otolaryngology department at CHC has conducted any research studies the effectiveness of different treatments of tracheostomy granulomas.

IV. Research Methods

A. Outcome Measure(s):

1. Success or failure of treatment method
 - a. Definition of success: We are defining successful treatment of tracheostomy granulomas as a clinically significant decrease in the size of granuloma (greater than 50% improvement) over a six week observation period using the assigned treatment.
 - b. Definition of failure: We are defining a treatment as a failure as if there is less than 50% reduction in size of tracheostomy granulomas at the conclusion of the six week observation period or if worsening occurs requiring alternative treatments.
2. Categorical Improvement (Degree of Improvement)
 - a. At each time point, the size of the granuloma will be measured and recorded. The percent circumference will also be measured
 - b. The approximate percent decrease in the granuloma size will be determined to determine the category subject's change in granuloma:
 - i. Complete resolution: >90% improvement (Score = 4)
 - ii. Improvement: 50 - 90% improvement (Score = 3)
 - iii. Minimal improvement: < 50% improvement (Score = 2)
 - iv. No improvement (Score = 1)
 - v. Worsening (Score = 0)

B. Description of Population to be Enrolled:

The population to be enrolled in this study includes all Children's Hospital Colorado patients, 31 days to 18 years of age inclusive, who are being treated for a tracheostomy granuloma and consent to participating in the study. We anticipate 45 patients will be needed for this pilot study to determine the effect size and variation in granuloma change.

C. Study Design and Research Methods:

The study will be a prospective comparison of three different treatment methods for patients with tracheostomy granulomas at Children's Hospital Colorado. The current standards of care for tracheostomy granulomas that we will be examining include: steroid application, silver nitrate and betadine. Patients or parents will be consented or assented during the initial physician visit prior to any administration of treatment by the provider. The treatment method will be assigned starting at the time the patient is enrolled in the study.

1. The three treatment methods (steroid application, silver nitrate, and betadine) will be assigned sequentially #1, #2, or #3. (See below for description)
2. Patients will be assigned a treatment method based on the sequential allocation done prior to enrollment. To reduce potential bias, the enrolling physicians will be unaware of the previous patient's allocated treatment group.
3. The treatment method for the patient given at the initial visit will be documented in Epic. During the six week observation period, the study team will collect follow-up data on the degree of improvement for each treatment method. Our primary time point will be 6 week follow up.
4. Each patient will be followed for an observation period of six weeks, with follow-up appointments, per standard of care, every two weeks (+/- 3 days) in order for a physician to evaluate the degree of improvement for each treatment method. If the investigator determines further follow-up is not necessary, per standard of care, the observation period will end.
5. If during a follow-up visit, the physician determines the patient's granuloma is worsening, the follow-up period will end and the patient's participation in the study will be complete. If

other treatments are utilized, we will analyze with the intent to treat analysis based on the treatment the subject was received.

[figure not shown]
6. In addition, if a patient is given a different form of treatment, such as in the emergency department or through a primary care physician, the follow-up period will end and the patient's participation in the study will be complete.

Treatments:

- 1) Silver nitrate – Silver nitrate will be applied to the tracheostomy site granuloma after enrollment. Parents will be instructed to keep the site dry for 14 hours. Residual granuloma will be treated similarly at Follow up #1 and #2, but not at Follow up #3.
- 2) Betadine solution will be used to topically treat the tracheostomy site BID for 2 weeks (until Follow up #1). If residual granuloma is present, an additional week will be recommended and this treatment duration recorded.
- 3) Hydrocortisone 1% topical will be used to topically treat the tracheostomy site BID for 2 weeks (until Follow up #1). If residual granuloma is present, an additional week will be recommended and this treatment duration recorded.

Study Design Flow Chart

Sequential allocation of treatment methods (steroid application, silver nitrate, or betadine)

Definition of success: We are defining successful treatment of tracheostomy granulomas as a clinically significant decrease in the size of granuloma (greater than 50 percent reduction) over a 6 week month period using the assigned treatment method.

Definition of failure: We are defining a treatment as a failure if after 6 weeks of treatment there is less than 50% reduction in the size of tracheostomy granulomas.

D. Description, Risks and Justification of Procedures and Data Collection Tools:

These methods of treatment do not represent a deviation of the standard of care for tracheostomy granulomas and incur the standard amount of risk.

The risks for administering steroid application include thinning of skin, local infection, and systemic absorption. Silver nitrate can cause superficial burning on normal tissue that is exposed. Betadine can cause skin irritation.

E. Potential Scientific Problems:

Potential scientific problems include the following:

1. Inability to enroll the number of patients needed to obtain data pertaining the success or failure of the three methods of treatment
2. Potential for bias in early failure between the 3 treatment arms. For example, it is possible that one treatment would work quickly and another would work slowly. If we discontinue follow-up too early, we would bias towards the early treatment effect. To minimize this risk we will continue to follow patients clinically with the treatment provided unless there is worsening of the granuloma that would require a change in treatment. There is the potential that this study is under powered. There is no data on the treatment of tracheostomy site granulomas and therefore the mean and variance in the treatment effect may be different than that estimated in our power analysis below. This study is powered to detect a clinically important difference and will additionally provide data to determine the sample size needed for future studies. We feel this potential is reasonable given that this study is a pilot study.

F. Data Analysis Plan:

Success and failure rates for each treatment method and the length of time between initial administration of the treatment and the determination of treatment success or failure will be utilized to compare the three standard of care treatment methods to better define and improve the current standard of care treatment of tracheostomy granulomas.

All variable will be analyzed for distribution and cleaned. For inconsistencies, we will refer back to the source data. Data will be checked for normalcy and non-parametric tests will be utilized for non-normal data. All analyses will utilize an alpha of 0.05 with two tails. The study will utilize an intent to treat analysis where subjects are analyzed according to the treatment they were assigned to regardless of treatments they receive.

Aim 1: Test for difference in treatment failure between the three treatment arms

Hypothesis 1: At the primary time point (6 weeks), there will be a clinically important difference between the silver nitrate treatment and the topical treatments.

Aim 2: Test for difference in categorical granuloma improvement in the three treatment arms

Hypothesis 2: At the primary time point (6 weeks), there will be more categorical improvement in the silver nitrate treatment group compared to and the topical treatments.

Aim 3: Describe the treatment effects of the three treatment arms including average number of treatments needed (silver nitrate), duration of topical medication administration (Betadine and Hydrocortisone, i.e. two weeks versus three weeks)

Hypothesis 3: Descriptive aim, no specific hypothesis in this pilot study.

Power Analysis:

Power analysis is based on aim 2. Because tracheotomy site granulomas have not been rigorously studied in the literature, the degree of improvement that will be found in the treatment groups is unclear. We hypothesize that the standard deviation for this 5 point scale will be one unit of measure. We determined the power to detect a difference of one unit of measure between treatment groups (from partial response to resolution or from minimal improvement to improvement). Assuming a sample size of 15 and an alpha of 0.05, our study will have an 80% power to detect a 1.1 point difference in categorical granuloma improvement. Table 1 below shows the power to detect differences between two treatment groups.

Table 1: Power analysis for Aim 2

Treatment A mean	Treatment B mean	% Diff	Power
3.4	2.4	42%	78%
3.4	2.2	55%	91%
3.4	2.1	62%	94%
3.5	2.5	40%	78%
3.6	2.5	44%	85%
3.7	2.5	48%	90%

The power to detect differences in treatment success (Aim 1) is shown in table 2. This study has an 80 percent power to detect a clinically important (50 percentage point) difference in treatment success between two treatment arms.

Treatment A Success (%)	Treatment B Success (%)	Relative Risk*	Power
60%	73%	0.67	12%
53%	73%	0.57	20%
47%	73%	0.5	30%
40%	73%	0.44	44%
33%	73%	0.4	60%
27%	73%	0.36	74%
20%	73%	0.33	87%

*protective effect of treatment B

G. Summarize Knowledge to be Gained:

Currently, there is no “gold” standard of care for the treatment of tracheostomy granulomas in children. The knowledge gained by comparing the effectiveness of different treatments will better define and improve the current standard of care. The knowledge to be gained will expectantly benefit future patients by reducing the frequency of recurring tracheostomy granulomas as well as minimizing office visits with inconsistent forms of treatment. This pilot study is powered to detect a clinically important difference in treatment effects with a modest sample size but additionally provide further estimates for sample sizes needed for future studies of this clinically important problem in pediatric otolaryngology.

H. References

1. Yaremchuk, K. Regular tracheostomy tube changes to prevent formation of granulation tissue. *The Laryngoscope* 2003;113:1-20
3. Al Samri M et al. Tracheostomy in children: a population based experience over 17 years. *Pediatric Pulmonology* 2010;45:487-493.
4. McShane Diana B and Jane S. Bellet. Treatment of Hypergranulation Tissue with High Potency Topical Corticosteroids in Children. *Pediatric Dermatology* Vol. 29 No. 5 675–678, 2012
5. Habif: *Clinical Dermatology*, 5th ed. Chap 27: Dermatologic Surgical Procedures

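### The Aim 2 analysis names no baseline covariate although granuloma size is recorded at each time point; adjusting the week-6 score for baseline size would cost little and would gain power if baseline is prognostic

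*Combined protocol and SAP*

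**What the plan says.** Section IV.A, item 2, provides for repeated measurement: "At each time point, the size of the granuloma will be measured and recorded". Percent circumference is recorded as well. The measurement then becomes a score: "The approximate percent decrease in the granuloma size will be determined to determine the category subject's change in granuloma". The five levels run from 4 (more than 90% improvement) down to 0 (worsening). Item 1 of the same section defines failure by a single cut, "less than 50% reduction in size of tracheostomy granulomas at the conclusion of the six week observation period", or by worsening that needs another treatment.

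Section IV.F tests these two derived outcomes at six weeks: "Aim 1: Test for difference in treatment failure between the three treatment arms" and "Aim 2: Test for difference in categorical granuloma improvement in the three treatment arms". The power analysis rests on Aim 2. The only guidance on method is "Data will be checked for normalcy and non-parametric tests will be utilized for non-normal data", together with two-sided alpha 0.05 and intention to treat. No test is named for either aim, and no covariate, regression model or analysis of measured size appears. Section IV.C describes sequential allocation without stratification on granuloma size.

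**The concern.** Baseline size is collected, but it enters the analysis only as the denominator of percent change. Dividing by baseline removes the dependence on baseline only if shrinkage is proportional to size. If small granulomas tend to resolve more completely than large ones, or the reverse, baseline size still predicts the score.

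Two things then follow. Outcome variation that a covariate could explain stays in the error term, which lowers power in a trial that section IV.E says may be underpowered. And if the arms happen to differ in baseline size, part of that difference carries into the week-6 comparison. With 15 per arm, such differences are not rare.

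**Working it through.** **1. The plan's own figures.** Inputs from IV.F: n = 15 per arm, SD = 1, two-sided alpha 0.05. The standard error of a difference is √(2/15) = 0.365. For a 1.0-point difference, 1.0/0.365 = 2.739, and Φ(2.739 − 1.960) = 78.2%; Table 1 states 78%. The six rows of Table 1 reproduce as 78.2, 90.8, 94.5, 78.2, 85.4 and 90.8%, against 78, 91, 94, 78, 85 and 90% stated. The formula is the ordinary unadjusted two-group one, which supports reading the planned comparison as unadjusted. There is no arithmetic error here.

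**2. How often the arms would differ at baseline.** This assumes allocation behaves as random. In SD units, the difference between two arm means has standard error 0.365. A gap above 0.5 SD has probability 2 × [1 − Φ(0.5/0.365)] = 17% for a given pair. By simulation of three arm means, it is 36% for at least one of the three pairs.

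**3. How much of a gap reaches the outcome.** The shift is correlation × gap × outcome SD. With an assumed percent-change SD of 40 points, a 0.5 SD gap shifts the comparison by 0.3 × 0.5 × 40 = 6 points at correlation 0.3, and by 0.5 × 0.5 × 40 = 10 points at correlation 0.5. The assumed effect is 40 points. At zero correlation the shift is zero.

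**4. Power for the 0-4 score, 15 v 15.** Assumed inputs: mean percent improvement 40 v 80, SD 40, capped at 100, cut into the protocol's five categories. The ranges are over repeated simulation runs.

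| Assumed baseline-outcome correlation | 0 | 0.3 | 0.5 |
|---|---|---|---|
| Score, unadjusted (Wilcoxon) | 67-69% | 68% | 67-68% |
| Score, baseline-adjusted rank ANCOVA | 67-69% | 71-72% | 77-78% |

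A second set-up used means 30 v 70, SD 40, a t test and ordinary ANCOVA on the score, with 20,000 runs. It gave 70.0, 69.5 and 69.9% unadjusted against 68.5, 71.4 and 78.4% adjusted. The loss at zero correlation is 70.0 − 68.5 = 1.5 points.

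**5. Analytic cross-check, continuous outcome with a 1 SD effect.** The noncentrality is 1 / [√(1 − ρ²) × √(2/15) × √(1 + 1/26)], on 27 degrees of freedom. Power is 73.6%, 77.5% and 84.9% at ρ = 0, 0.3 and 0.5, against 75.3% for the unadjusted t test. The loss at ρ = 0 is 1.7 points, close to step 4.

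**6. Type I error.** With no treatment effect, rejection rates over all simulated trials were 4.2% to 5.5%, whether or not the analysis was adjusted. Among trials with a baseline gap above 0.5 SD and correlation 0.5, the unadjusted score rejected in 9.7% and 11% of cases in two separate runs, against 4.5% to 4.9% adjusted. At correlation 0.3 the unadjusted rate in such trials was about 6%.

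**7. Cost of the five-level cut itself.** In the second set-up, unadjusted and at zero correlation, measured percent change had 74% power and the score 70%, a loss of about 4 points.

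**The case against.** The strongest reply is that the benefit depends on a correlation the documents do not give. Percent change may already remove most of the baseline effect. At correlation 0.3 the gain is only about 3 points, and at zero there is a small loss. This stands, and it is why the point concerns efficiency rather than error. The second reply is that the plan does not choose an unadjusted test; it names no test at all. This also stands: the reading rests on silence and on the formula that reproduces Table 1.

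A reader might infer three stronger claims, and the documents support none of them.

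- **That the unadjusted comparison is invalid.** Its error rate already allows for chance imbalance and is close to 5% over all trials. The excess appears only within trials that turn out imbalanced, and only if baseline is prognostic.
- **That scoring wastes much of the data.** The five-level cut costs a few points. The yes/no outcome loses more (56% against 74% for measured change in the second set-up), but that scenario is a success difference of about 38 points (69% v 31%). Table 2 openly shows 44% power for 40% v 73% and 60% for 33% v 73%. Success is also the authors' clinical definition.
- **That Aim 1 should become descriptive, with measured percent change taking its place.** That would drop a prespecified test. A percent-change analysis would also need a rule for children whose participation ends early under IV.C, items 4 to 6. The plan has none, and IV.A itself calls the percent decrease approximate.

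**Conclusion.** The point holds as a modest, low-cost improvement to Aim 2. Power for the score is unchanged or slightly lower at zero correlation, about 3 to 4 points higher at 0.3 and about 10 higher at 0.5. Adjustment also keeps the error rate near 5% in a trial that happens to be imbalanced at baseline. These sizes rest on assumed means, an assumed SD of 40, an assumed range of correlations, and allocation that behaves as random. The stated powers are correct, and the unadjusted test is valid on average.

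**What to change.** In IV.F, prespecify the Aim 2 analysis as the week-6 0-4 score on arm plus baseline granuloma size, by a proportional-odds model or a rank ANCOVA. Name one of the two before data are examined. The power figures above are for the rank ANCOVA. Keep children who leave for worsening at score 0, as the scale already defines, so the main change needs no imputation for them. Children whose participation ends for other reasons need a stated rule with or without the covariate.

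Keep the Aim 1 success/failure test as planned. A baseline-adjusted rank analysis of measured percent change may be added as optional and supportive only, ranking children who leave for worsening lowest.

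The cost is a few lines of text and one degree of freedom, about 1.5 points of power if baseline size is not prognostic. No new data, visits or patients are needed. The fitted baseline effect would also help to size the later studies that section IV.G has in view.

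### Treatments are allocated sequentially with no random element stated, so an enrolling physician who knows the order and the current position can foresee the next arm

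*Combined protocol and SAP*

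**What the plan says.** Section IV.C, item 1: "The three treatment methods (steroid application, silver nitrate, and betadine) will be assigned sequentially #1, #2, or #3". Item 2: "Patients will be assigned a treatment method based on the sequential allocation done prior to enrollment". The label of the Study Design Flow Chart again calls the allocation sequential. The design is described as a prospective comparison. No section mentions randomization, a random list, blocks, envelopes, central release or a holder of the list.

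Item 2 gives one safeguard: "the enrolling physicians will be unaware of the previous patient's allocated treatment group". It does not say how this will be achieved. Item 3 adds: "The treatment method for the patient given at the initial visit will be documented in Epic".

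Section I reports a survey of the thirteen attendings at the hospital and its satellite clinic, in which silver nitrate was the most commonly preferred treatment (75%). In section IV.F, Aims 1 and 2 test differences between arms, and "All analyses will utilize an alpha of 0.05 with two tails". No baseline adjustment is planned.

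**The concern.** Consent is sought at the physician visit. A physician who can foresee the next arm can influence, knowingly or not, which patient is approached and when. A difference between arms may then partly reflect who was enrolled into each arm. The nominal 5% error rate for Aims 1 and 2 is no longer protected, and enrolling more patients would not cure the bias. The protocol also intends its estimates to inform sample sizes for later studies, and between-arm effect sizes would carry the same bias forward. The descriptive Aim 3 is less affected.

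The stated safeguard hides the position in the sequence but does not make the order unpredictable. It is fragile here: clinic-applied silver nitrate and twice-daily topical treatment at home are easily told apart, treatment is in the medical record, and a physician who enrols consecutive patients knows the previous arm. The survey preference supplies a possible motive.

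**Working it through.** **Inputs from the protocol.** 45 patients (IV.B); 15 per group, and for Aim 2 "We hypothesize that the standard deviation for this 5 point scale will be one unit of measure" (Power Analysis); two-sided alpha 0.05 (IV.F).

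**The plan's own power figures, as the baseline for the cost of a change.**
- Aim 1, 50 percentage points, for example 25% v 75%: Φ[(0.5 − 1.96·√(2·0.5·0.5/15)) / √((0.1875 + 0.1875)/15)] = Φ[(0.5 − 0.358)/0.158] = 0.816. For lower rates of 20% to 30% the result is 0.816 to 0.820; the plan states 80%.
- Aim 2, 1.0 point: Φ[1/√(2/15) − 1.96] = Φ(0.779) = 0.782; Table 1 states 78%.

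Both depend on 15 per arm, not on how the order is generated. A blocked list that ends at 15 per arm leaves them unchanged.

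**Chance of predicting the next arm.**
- Rotation, order and position known: 100%.
- Rotation, order and own last arm known. Assume the physician enrols an independent share p of patients. The best guess is the next arm in the cycle, and it is right with probability a = p/(1 − (1 − p)³). This gives 36% for p = 1/13, 47% for 1/3, 57% for 1/2 and 100% for consecutive patients.
- Random blocks of 3 and 6 with equal probability, full history known, guessing the least-used arm (20,000 simulated lists of 45): about 57%.
- Random list, past assignments hidden: 33%.

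**Effect on the error rate.** Assume no true effect, and that patients with a prognosis better by e points are enrolled whenever silver nitrate is predicted. The plan names no test, so a two-sample t test is used (15 per arm, SD 1, 28 df, critical value 2.048).
- The standard error is √(2/15) = 0.365.
- Under a known rotation the imbalance is e. The noncentrality is 0.25/0.365 = 0.685 or 0.5/0.365 = 1.369, giving two-sided errors of 10.1% and 26.2%.
- Under partial knowledge, silver nitrate is predicted with probability a when it is the true next arm, and with a(1 − p) or a(1 − p)² when another arm is. For p = 1/2 these are 4/7, 2/7 and 1/7. With e = 0.5 the imbalances are 0.5 × 2/7 = 0.143 and 0.5 × 3/7 = 0.214, giving 6.7% and 8.8%.

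| Situation | Next arm predicted | Error, e = 0.25 | Error, e = 0.5 |
|---|---|---|---|
| Rotation, order and position known | 100% | 10.1% | 26.2% |
| Rotation, own last arm known, enrols 1 in 2 | 57% | 5.4–5.9% | 6.7–8.8% |
| Same, enrols 1 in 3 | 47% | 5.1–5.4% | 5.5–6.4% |
| Same, enrols 1 in 13 | 36% | 5.0% | 5.0–5.1% |
| Blocks of 3 and 6, full history known (simulated) | 57% | 6% | 7% |
| Concealed random list (simulated) | 33% | 5% | 5% |

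Ranges cover silver nitrate against each of the other two arms. The block and concealed-list error rates come from 8,000 simulated trials per case.

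**Why blocks.** Simple randomization of 45 leaves the smallest arm below 12 in about 39% of lists.

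**The case against.** The strongest reply is that the 10% and 26% figures require the safeguard in item 2 to fail completely, for every enroller and all 45 patients. That is right. With partial leakage and no physician enrolling more than 1 in 3 patients, the error rises by at most about 1.4 percentage points. That is no worse than blocks of 3 and 6 whose full history is known. A rotation whose position stays hidden is also guessed only 33% of the time, so much of the contrast measures concealment rather than randomness. This tempers the size of the problem. It does not remove it, because the protocol gives no mechanism for hiding the position.

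Other points:
- The wording could mean taking the next entry from a prepared list that was itself random. No cycle is written out, so this is possible, but the text does not say it.
- Consent precedes treatment, and assignment starts at enrolment (IV.C). This does not prevent prediction from a known order.
- The survey asked which method attendings thought most successful, not whom they would enrol, and the hypotheses in sections I and IV.F point in different directions. The direction of any steering is therefore an assumption.
- Both outcomes are measured as change from the patient's own granuloma size. This partly accounts for baseline size but not for other prognostic factors.
- This is a pilot, and variance estimation is less exposed. It nevertheless claims power for between-arm tests.

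**Conclusion.** The concern holds. The protocol states a sequential allocation three times and a random element nowhere, and its single safeguard has no mechanism. The next arm is fully predictable if order and position are known. The error rate is then about 10% or 26% under assumed prognostic shifts of 0.25 or 0.5 points, and about 5% to 9% under the partial-knowledge cases. These figures illustrate exposure; they do not estimate what happened, and the documents show no steering. The fixed rotation is the natural reading rather than a stated fact, but the same edit is needed if a random list was intended. It should be made because no later analysis can reliably restore unpredictable assignment, and the cost is very small. The protection needs the list to be both random and concealed.

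**What to change.** Replace items 1 and 2 of section IV.C with:

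*Participants will be assigned 1:1:1 to silver nitrate, betadine or steroid application from a computer-generated list in random permuted blocks of varying size. A person who does not enrol patients will prepare and hold the list. Each assignment will be identified by treatment name and revealed (sealed opaque envelope or electronic release) only after consent is recorded.*

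Use blocks of 3 and 6 in random order, with the sizes recorded only where enrolling physicians do not see them. Keep the sentence on physicians being unaware of the previous arm as an added safeguard. Change the flow-chart label to match. Use treatment names rather than numbers, because item 1 lists the steroid first while the Treatments list numbers silver nitrate as 1.

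The cost is one paragraph, one label, a list made once and one non-enrolling person to hold it. There are no extra patients or visits. The downside is that about 20% of 3/6-block lists cut at 45 give arms of 16/15/14. Fixing the list to end on a complete block at 45 avoids this if enrolment reaches 45; for example, five blocks of 6 and five of 3 in random order give 30 + 15 = 45.

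### Protocol IV.D names five treatment risks, but no outcome, follow-up item, aim or analysis plans to record or describe any of them by arm

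*Combined protocol and SAP*

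**What the plan says.** **Risks named.** Section IV.D gives three for the steroid: "The risks for administering steroid application include thinning of skin, local infection, and systemic absorption". For the other two arms it says: "Silver nitrate can cause superficial burning on normal tissue that is exposed. Betadine can cause skin irritation". Section II describes the overall burden as small: "Each treatment has minimal morbidity and side effects".

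**Data planned.** IV.C item 3 states that "the study team will collect follow-up data on the degree of improvement for each treatment method". Item 4 gives the two-weekly visits the same purpose: "in order for a physician to evaluate the degree of improvement for each treatment method". Both outcomes in IV.A (success or failure, and the 0 to 4 score) are defined by change in the granuloma. IV.A also has percent circumference measured. The treatment descriptions in IV.C have the duration of topical treatment recorded. IV.F adds time to success or failure, and Aim 3 adds the number of silver nitrate treatments.

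**Use of the result.** IV.G says: "The knowledge gained by comparing the effectiveness of different treatments will better define and improve the current standard of care". IV.F states the same purpose.

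**The concern.** The three arms carry different named risks, and the plan intends its comparison to inform which treatment becomes standard. Run as written, it can rank the arms on shrinkage but has no data to set beside that ranking on burns, irritation, infection or skin thinning. The statement in Section II that side effects are minimal would remain untested. A pilot meant to inform later trials would supply no harm counts.

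There is also a problem for a planned result. Aim 3 describes how many silver nitrate treatments were needed and whether topical treatment lasted two or three weeks. If an application was withheld because of a burn, or a topical was cut short because of irritation, the smaller figure would enter Aim 3 with no reason attached. A poorly tolerated treatment could then look like one of which little is needed.

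**Working it through.** **Step 1. Count the named risks (IV.D).** Steroid 3 + silver nitrate 1 + betadine 1 = 5.

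**Step 2. Look for them in everything the plan measures or analyses.**

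| Place | What is captured | Any of the five risks? |
|---|---|---|
| IV.A outcome 1 | Success or failure by granuloma size, or worsening that needs another treatment | No |
| IV.A outcome 2 | Five-level score of granuloma change; percent circumference | No |
| IV.C items 3 and 4 | Degree of improvement | No |
| IV.C treatment descriptions | Duration of topical treatment | No |
| IV.F opening paragraph | Success and failure rates; time to either | No |
| Aim 1 | Treatment failure | No |
| Aim 2 | Categorical improvement | No |
| Aim 3 | Number of silver nitrate treatments; topical duration | No |

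That is 0 of 2 outcomes and 0 of 3 aims. Worsening (score 0) is worsening of the granuloma. A child with more than 50% shrinkage and a burn is scored the same as one with that shrinkage and no burn.

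**Step 3. Confirm the arm size from the plan's own figures.** IV.B gives 45 children in three arms, so 45/3 = 15, and the power analysis uses 15. For Aim 1 the plan states 80% power for a 50-point difference. By the pooled normal approximation,

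power = Φ{[d√n − 1.96√(2p̄(1−p̄))] / √(p₁(1−p₁) + p₂(1−p₂))}.

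With n = 15 and 25% vs 75%: (0.5 × 3.873 − 1.96 × 0.707)/0.612 = 0.90, so power is 81.6%, which agrees with the stated 80%. All seven rows of the Aim 1 power table also reproduce at 15 per arm (11.6, 20.0, 31.3, 45.0, 60.2, 75.0 and 87.4%, against 12, 20, 30, 44, 60, 74 and 87%).

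**Step 4. What 15 per arm could show if harms were recorded.** The documents give no harm rates, so the rates below are assumptions.

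- Chance of at least one event in an arm, 1 − (1 − p)^15: 14% at p = 1% (1 − 0.99^15 = 0.140), 54% at 5% (1 − 0.95^15 = 0.537), 79% at 10% (1 − 0.90^15 = 0.794).
- Upper limit after 0 of 15: one-sided 95%, 1 − 0.05^(1/15) = 18.1%; two-sided 95% exact, 1 − 0.025^(1/15) = 21.8%.
- Power for a pairwise test of 5% vs 20%: 23% by the pooled normal formula and 8% by Fisher's exact test. About 76 per arm would be needed for 80% power (pooled normal).

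Recording harms would therefore give useful counts but not a formal comparison.

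**The case against.** The best defence is scope. This is a small pilot of treatments that IV.D describes as within standard care, and its stated purpose is to compare effectiveness. The sentence in IV.G speaks of effectiveness and claims nothing about harm. Fifteen per arm could not compare uncommon harms in any case, and every harm rate in the working is assumed.

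Much of this stands. It rules out a formal test of harms and keeps the point modest. It does not justify leaving harms out of the data. That the treatments are standard supports offering them, but does not show how their harms compare. A physician is already due to see each child every two weeks.

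Several stronger readings are tempting and should be set aside:

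- *Follow-up data are restricted to improvement.* Item 3 says what will be collected, not that nothing else will be. Percent circumference, treatment number and duration, and time to outcome are also planned. None of them is a harm.
- *A withheld treatment would leave no trace.* It would change the Aim 3 figures, and a switch to another treatment would show as an early exit under IV.C item 6. What is lost is the reason.
- *Treatment is repeated on residual granuloma and nothing else.* IV.C makes residual granuloma the trigger, but does not say that other findings are ignored.
- *The trial would redefine standard care.* The stated purpose is to define it better and improve it.
- *Bleeding, obstruction and respiratory distress are unrecorded treatment harms.* Section II attributes these to the granulation tissue.

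Consent pages and one figure are absent from the text available, so any safety wording there cannot be checked. The outcome, follow-up and analysis sections are present and contain no harm measure.

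**Conclusion.** The point holds as a cheap improvement. Five risks are named and none is planned to be recorded or described by arm. As specified, the study data could not describe harms by arm, and low treatment counts or short durations in Aim 3 could not be separated from treatment cut back because of a reaction.

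The size of the gap cannot be put as an error in any planned estimate, because the documents give no harm rates. The figures above only bound what the fix can deliver: a harm with an assumed rate of 10% would probably appear at least once in an arm (79%), one with an assumed rate of 5% about half the time (54%), and a clean record in 15 children would still be compatible with rates up to about 22%. These figures assume 15 children observed per arm. Early exits under IV.C items 4 to 6 would shorten observation, possibly unequally between arms.

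A reader might infer that children would be exposed to harms nobody notices. The documents do not support that: physicians review the children, and clinical charting may well record reactions. The finding concerns what enters the study data.

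**What to change.** 1. **IV.C item 3:** widen the follow-up data to degree of improvement and local treatment harms. At each existing two-week visit record yes/no and date for local infection, skin thinning, burn of normal tissue and skin irritation.
2. **Reasons:** record why whenever assigned treatment is withheld, stopped or switched, or participation ends, taken from the study chart where available. Information held by emergency departments or primary care cannot be assumed to reach the study.
3. **Granuloma complications:** record bleeding, obstruction and respiratory distress separately, not as treatment harms.
4. **Aim 3:** add counts of each harm by assigned arm with exact 95% intervals and observed follow-up time, descriptively and without tests.
5. **IV.G:** state that 15 per arm cannot rule out uncommon harms (0 of 15 leaves rates up to about 22% possible) and that systemic absorption was not measured.

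The cost is a few minutes per visit, one table and a wording amendment. The downside is that the harm judgements are unmasked and can only be described. No treatment, schedule or clinical rule changes.
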